1.3 Rationale for conducting this study

Uncontrolled diabetes patients are treated not by switching medications but by adding on therapies. Double-combination of metformin and sulfonylurea is highly common in Asia Pacific and the United Kingdom, with a high proportion of patients being uncontrolled

and needing a third drug. The addition of saxagliptin to the metformin and sulfonylurea combination could improve the control of diabetes.

There is an unmet need with the current pharmacological treatment of type 2 diabetes. Despite available drugs with different mechanisms of actions, many patients are not reaching glycaemic control goals. Some insulin secretagogues have significant side effects such as hypoglycaemia, weight gain and insulin resistance.

The purpose of this 24-week Phase IIIb clinical study is to determine whether the addition of saxagliptin to a double-combination of metformin and sulfonylurea will provide better glycaemic control, and to compare the safety and tolerability profiles of the two treatment groups (placebo versus saxagliptin as add on therapy to double-combination of metformin and sulfonylurea), in patients with type 2 diabetes.

1.4 Benefit/risk and ethical assessment

For an overall risk/benefit assessment of saxagliptin, see the Investigator's Brochure ([Investigator's Brochure](#)).

A total of 5346 subjects were evaluated in the saxagliptin Phase I to III clinical development programme, including 423 in a Phase IIb dose-ranging study and 4250 subjects in Phase III studies. In the development programme, saxagliptin was studied at maximum daily doses of 400 mg (80-fold the Recommended Usual Clinical Dose [RUCD]) for up to 2 weeks, 100 mg (20-fold the RUCD) for up to 6 weeks, 40 mg (8-fold the RUCD) and 20 mg (4-fold the RUCD) for up to 12 weeks, and 10 mg (2-fold the RUCD) for up to 2 years. Saxagliptin doses of 2.5 mg and 5 mg have also been studied for up to 2 years. As of October 2008, the total number of subjects in the Phase IIb/III studies exposed to saxagliptin (2.5 mg, 5 mg, or 10 mg) for ≥ 50 weeks included 652 subjects treated with saxagliptin monotherapy, 902 subjects treated with saxagliptin in combination with metformin, 407 subjects treated with saxagliptin added on to sulfonylurea, and 275 subjects treated with saxagliptin added on to thiazolidinedione.

In summary, the safety and efficacy data collected to date from clinical studies in healthy volunteers and patients with type 2 diabetes indicate that the clinical safety and efficacy profile of saxagliptin support studies with 5 mg as the usual recommended dose. It is hypothesised that saxagliptin has a comparable safety and tolerability profile compared to metformin with regards to hypoglycaemic events. Studies on the long-term cardiovascular safety profile of saxagliptin are currently ongoing.

Increased incidence of gastrointestinal distress has previously been noted with metformin therapy.

The incidence of hypoglycemia was numerically higher for subjects who received saxagliptin 5 mg when added to an intermediate dose of SU compared with uptitration of SU monotherapy in study CV181040 (add-on combination therapy with glyburide in subjects who have inadequate glycaemic control on submaximal SU dose).

2. STUDY OBJECTIVES

2.1 Primary efficacy objective

The primary efficacy analysis is to compare the difference between saxagliptin 5 mg od plus metformin plus sulfonylurea versus placebo plus metformin plus sulfonylurea, in patients with type 2 diabetes, as determined by the change in HbA_{1c} levels from Baseline to Week 24/Endpoint.

2.2 Secondary efficacy objectives

- Compare change in fasting plasma glucose (FPG) from Baseline to Week 24/Endpoint between the treatment groups;
- Compare change in postprandial glucose (PPG) (measured 2 hours after breakfast) from Baseline to Week 24/Endpoint between the treatment groups;
- Compare proportion of patients achieving a therapeutic glycaemic response at Week 24/Endpoint defined as HbA_{1c} <7% between the treatment groups.

2.3 Safety objectives

Safety and tolerability will be evaluated by assessment of:

- All AEs, including hypoglycaemic events
- Laboratory values
- Changes in renal function by estimation of CrCl (Cockcroft Gault) and urinary albumin:creatinine ratio
- 12-Lead electrocardiogram (ECG)
- Vital signs (pulse and blood pressure)
- Body weight
- Physical examination

2.4 Other objectives

- To compare change in total cholesterol (TC), low-density lipoprotein-cholesterol (LDL-C), high-density lipoprotein-cholesterol (HDL-C) and triglycerides (TG), from Baseline to Week 24/Endpoint
- To compare patient related endpoints using the EuroQoL-5 Dimension (EQ-5D) questionnaire.

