Figure 1 Study flow chart for screening, enrolment period and double-blind treatment period

MTD: Maximum tolerated dose

* Minimum dose of metformin for enrolment = 1500 mg

** Minimum dose for sulfonylurea for enrolment is 50% of the maximum recommended dose:

Note: Patients will continue taking metformin and sulfonylurea at doses ascertained at enrolment, during the double-blind treatment period. Saxagliptin and Placebo will be administered as add-on therapy.

In this study, each patient will be enrolled on a stable combined dose of metformin XR or IR (MTD, with minimum dose for enrolment being 1500mg) and sulfonylurea (MTD, with minimum dose for enrolment being $\geq 50\%$ of the maximum recommended dose) for at least 8 weeks prior to Visit 1.

.Note: Patients must be on MTD of metformin IR or XR (minimum dose for enrolment being 1500 mg) and on MTD of sulfonylurea (minimum dose for enrolment being 50% of maximum recommended dose).

Following Informed Consent, patients will be pre-screened for HbA_{1c} – at Visit 1, within 14 days prior to randomisation. Patients whose HbA_{1c} is $\geq 7\%$ and $\leq 10\%$, as confirmed by central laboratory, will undertake safety and other assessments at Visit 2 (Day -7) to confirm remaining eligibility criteria. Patients who meet all of the inclusion criteria and none of the exclusion criteria will be randomised at Visit 3 and will commence the 24-week double-blind treatment period.

During the 24-week double-blind treatment period of the study, patients will still receive metformin and sulfonylurea at the dose ascertained during enrolment. In addition, patients will be randomised, at Visit 3, to receive the following:

- Double-blind saxagliptin 5 mg, orally, od or
- Double-blind matching placebo orally, od.

The study will consist of two periods:

Screening/enrolment period

Patients with type 2 diabetes who have inadequate glycaemic control (HbA_{1c} $\geq 7\%$ and $\leq 10\%$) and are currently on a stable combined dose of metformin XR or IR (MTD) and sulfonylurea (MTD) for at least 8 weeks prior to Visit 1 are eligible for enrolment. Blood samples for assessment of inclusion and exclusion criteria will be taken at Visit 1 and Visit 2 and assessed at the central laboratory before randomisation

Randomisation and double-blind treatment period

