4.1 Inclusion criteria

For inclusion in the study subjects should fulfil all the following criteria:

1. Provision of written informed consent prior to the performance of any study-related procedures.
2. Males and females who are ≥ 18 years of age at the time of obtaining consent at Visit 1.
3. Clinical diagnosis of type 2 diabetes with uncontrolled glycaemia in spite of being on the combination of metformin IR or XR (MTD, minimum dose for enrolment being 1500mg) plus sulfonylurea (at MTD, with minimum dose for enrolment being $\geq 50\%$ of the maximum recommended dose) daily for at least 8 weeks prior to Visit 1.
4. $HbA_{1c} \geq 7\%$ and $\leq 10\%$ obtained at Visit 1 as confirmed by the central laboratory.
5. $BMI \leq 40 \text{ kg/m}^2$.
1. Females of childbearing potential must be using an adequate method of contraception to avoid pregnancy throughout the study and for up to 4 weeks after the study in such a manner that the risk of pregnancy is minimised, and have a negative urine pregnancy test at Visit 2 and each scheduled study visit thereafter.

Definitions:

- **Females of Child Bearing Potential** – women who have experienced menarche but who have not been permanently or surgically sterilised, are not postmenopausal and are capable of procreation.
- **Females NOT of Child Bearing Potential** - women who have undergone successful surgical sterilisation (hysterectomy, bilateral tubal ligation or bilateral oophorectomy) or who are postmenopausal.
- **Postmenopausal Women** – women will be considered postmenopausal if they have had amenorrhea ≥ 12 consecutive months; or women on hormone

replacement therapy (HRT) with documented serum follicle stimulating hormone (FSH) level >35 mIU/mL

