6.4.5 Laboratory safety assessment

Blood and urine samples for determination of clinical chemistry, haematology and urinalysis tests will be taken at the times indicated in [Table 3](#). The date and time of sampling will be recorded on the laboratory requisition form. The samples will be processed by the central laboratory and results will be reported back to the study centre within 72 hours.

All samples should be taken by adequately trained study personnel, and performed and handled in accordance with given instructions in the Laboratory Manual. Up to date reference ranges will be provided during the study and laboratory results will be compared to the laboratory standard normal ranges and flagged if they are outside the normal range. The investigator should make an assessment of the available results with regard to clinically significant abnormalities. The laboratory reports should be signed and retained at the study centre as source data for laboratory variables.

For information on how AEs based on laboratory tests should be recorded and reported, see [Section 6.4.3](#).

The complete list of safety laboratory variables is displayed in [Table 3](#).

Table 3 Safety laboratory variables

Visit number	1	2	3	4	5	6	7	8	9
Study Week	-2	-1	1	4	8	12	16	20	24
Study Day	-14	-7	1	28	56	84	112	140	168
Haematology									
Haemoglobin		X	X			X			X
Haematocrit		X	X			X			X
Red blood cell count		X	X			X			X
White blood cell count and differential		X	X			X			X
Platelet count		X	X			X			X
Clinical chemistry									
Aspartate aminotransferase (AST)		X	X			X			X
Alanine aminotransferase (ALT)		X	X			X			X
Alkaline phosphatase		X	X			X			X
Creatine kinase (CK)		X	X			X			X
Total bilirubin		X	X			X			X
Total protein		X	X			X			X
Albumin		X	X			X			X
Blood urea nitrogen (BUN)		X	X			X			X
Electrolytes:		X	X			X			X
- Sodium									
- Potassium									
- Chloride									
Serum creatinine (SCr) for estimation CrCl (Cockcroft Gault)		X	X			X			X

Visit number	1	2	3	4	5	6	7	8	9
Study Week	-2	-1	1	4	8	12	16	20	24
Study Day	-14	-7	1	28	56	84	112	140	168
Thyroid stimulating hormone (TSH) ^a			X						
Follicle stimulating hormone (FSH) ^b			X						
Total Cholesterol									X
HDL-C			X						X
LDL-C			X						X
TG			X						X
Urinalyses									
pH		X	X			X			X
Protein ^c		X	X			X			X
Glucose		X	X			X			X
Leukocyte esterase ^c		X	X			X			X
Blood by dipstick ^c		X	X			X			X
Pregnancy test ^d		X	X	X	X	X	X	X	X
Albumin:creatinine ratio		X	X			X			X

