a. If abnormal, refer to free levothyroxine (T₄).

b. For women on hormone replacement therapy.

c. Microscopy if dipstick positive for blood, leukocyte esterase or protein.

d. Urine beta human chorionic gonadotropin (hCG) pregnancy test for women of childbearing potential (hCG minimum sensitivity of 25 IU/L) (dipstick analysed at the study centre).

For blood volume collected, see Section 7.1

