11. EVALUATION AND CALCULATION OF VARIABLES

11.1 Calculation or derivation of efficacy variables

11.1.1 Baseline and Change from Baseline

Baseline is defined as the last non-missing value before the first dose of double-blind treatment on Week 1 (Day 1). Change from Baseline will be calculated as:

Change from Baseline at Week 24/Endpoint = (Value at Week 24/Endpoint – Baseline value).

The Endpoint value for the primary or secondary efficacy parameters will be derived using the last observation of the double-blind randomised treatment period (from first administration of double-blind investigational product to last administration of double-blind investigational product) carried forward.

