12.2 Methods of statistical analyses

12.2.1 Efficacy

The primary objective of this study is to compare the difference between saxagliptin and placebo as add-on therapy to combination metformin and sulfonylurea in the change in HbA_{1c} levels from Baseline to Week 24/Endpoint.

The null hypothesis H₀ given below will be tested against the alternative hypothesis H_A ($\alpha=0.05$, two-sided). For saxagliptin the alternative hypothesis states that the difference in the mean change from Baseline to Week 24/Endpoint and placebo is not zero:

$$H_0: \mu_T - \mu_P = 0 \quad \text{versus} \quad H_A: \mu_T - \mu_P \neq 0$$

where μ_T denotes the mean change in HbA_{1c} from Baseline to Week 24/Endpoint in the group of patients treated with saxagliptin (active investigational product, T) and μ_P the mean change in HbA_{1c} from Baseline to Week 24/Endpoint in the group of patients with placebo (comparator, P).

The change from Baseline to Week 24/Endpoint in HbA_{1c} will be analysed using an analysis of covariance (ANCOVA) model with treatment group and country as factors and Baseline HbA_{1c} as a covariate. Missing Week 24 values will be replaced using the last observation carried forward (LOCF) after baseline. The model will be used to derive a least squares estimate of the treatment difference in mean change with corresponding two-sided 95% confidence interval (CI) and two-sided p-value. Further, two-sided 95% CIs for the mean change within each treatment group will be calculated.

The LOCF approach means that Week 24/Endpoint analyses will be based on measurements available at Week 24 or the last post-baseline measurement prior to Week 24, if no measurement is available at the Week 24 time-point.

Continuous secondary and other relevant variables will be analysed by means of an ANCOVA for change from baseline to Week 24 using treatment group and country as factors and their baseline value as a covariate. By analogy to the primary efficacy variable, the LOCF method will be applied and the model will be used to derive point estimates and two-sided 95% confidence intervals for the mean change within each treatment group as well as for the difference in mean change between the two treatment groups. Nominal two-sided p-values for the difference between the treatment groups will be provided.

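### Table 3 schedules total cholesterol at Visit 9 only, so its planned change from Baseline has no baseline value if the schedule is followed as written

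*Protocol*

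**What the plan says.** The Synopsis (under other objectives and again under other endpoints) and Section 2.4 name four lipids and treat them alike: "To compare change in total cholesterol (TC), low-density lipoprotein-cholesterol (LDL-C), high-density lipoprotein-cholesterol (HDL-C) and triglycerides (TG), from Baseline to Week 24/Endpoint".

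Section 11.1.1 fixes what counts as baseline: "Baseline is defined as the last non-missing value before the first dose of double-blind treatment on Week 1 (Day 1"). Section 12.2.1 gives the model: "Continuous secondary and other relevant variables will be analysed by means of an ANCOVA for change from baseline to Week 24". Its terms are treatment group and country as factors and the variable's own baseline value as covariate.

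The sampling schedule is in Table 3, Section 6.4.5. The row "Total Cholesterol" has a single mark, at Visit 9. The HDL-C, LDL-C and TG rows directly below it each have two marks, at Visits 3 and 9.

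On the side point, Table 3 marks "Follicle stimulating hormone (FSH") at Visit 3 only, with the footnote "For women on hormone replacement therapy". Section 4.1 uses that test in its definition of postmenopausal: "replacement therapy (HRT) with documented serum follicle stimulating hormone (FSH) level >35 mIU/mL". Section 3.1 sets the timing of eligibility bloods, with randomisation as the limit (the word that completes this sentence in the protocol): "Blood samples for assessment of inclusion and exclusion criteria will be taken at Visit 1 and Visit 2 and assessed at the central laboratory before".

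**The concern.** A change from baseline needs two measurements, and the schedule provides one. The Visit 9 sample is taken at the end of treatment and cannot meet the baseline definition. Without a pre-dose value neither the response variable nor the covariate of the planned ANCOVA exists for total cholesterol.

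The loss would be permanent. Section 7.3 says samples are disposed of after analysis, so a missed Visit 3 assay could not be run later from stored material. The statistical analysis plan was not available for this review, but no analysis plan can supply a sample that was never scheduled.

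**Working it through.** No power or sample-size figure is involved. The check is a reading of the schedule against the definitions.

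**Step 1: which visits each row of Table 3 marks** (columns are Visits 1 to 9).

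| Row in Table 3 | Visits marked | Pre-dose value? | Week 24 value? |
|---|---|---|---|
| Total cholesterol | 9 | No | Yes |
| HDL-C | 3, 9 | Yes | Yes |
| LDL-C | 3, 9 | Yes | Yes |
| TG | 3, 9 | Yes | Yes |
| Serum creatinine (for comparison) | 2, 3, 6, 9 | Yes | Yes |
| FSH (women on hormone replacement) | 3 | n/a | n/a |

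A Visit 3 sample does qualify as baseline. Sections 5.5.2 and 6.3.1 have the morning dose taken after the laboratory specimens are collected.

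**Step 2: is a pre-dose total cholesterol scheduled anywhere else?** Table 1 has only a general laboratory row and refers to Sections 6.3.1 and 6.4.5 for the parameters. Table 2 (Section 6.3.1) lists no lipids. Section 6.4.5 describes Table 3 as the complete list of safety laboratory variables. Table 4 gives volumes by type of sample and names no lipid. The answer is no.

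**Step 3: can the planned handling of missing data help?** Section 12.2.1 carries post-baseline values forward to Week 24. It does not create a baseline value.

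**Step 4: size.** Followed as written, the number of patients with a computable change in total cholesterol is 0 of the 250 to be randomised. If the laboratory reports total cholesterol at Visit 3 anyway, for example because LDL-C is calculated from it, the number is the same as for the other three lipids. The protocol does not say whether LDL-C is measured directly or calculated, so both ends of that range are open.

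**Step 5: is there room to add the test?** Table 4 counts four clinical chemistry samples of 10 mL each (4 × 10 = 40 mL). Four matches the chemistry visits in Table 3, namely 2, 3, 6 and 9. Table 4 has no separate line for lipids, so the three already drawn at Visit 3 appear to come from that sample, and total cholesterol can join them.

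**Step 6: the FSH side note.** Section 3.1 puts blood samples for eligibility at Visits 1 and 2, to be assessed before randomisation. FSH bears on a definition under an inclusion criterion and is marked at Visit 3, the randomisation visit. Section 6.4.5 allows up to 72 hours for results. The timing therefore does not match Section 3.1. What follows from this depends on the default in Section 4.1. A woman who is neither sterilised nor postmenopausal falls in the childbearing group. Hormone replacement moves her to postmenopausal through FSH only once a value above 35 mIU/mL is documented. Until then, unless the separate amenorrhoea arm applies, contraception and the pregnancy tests from Visit 2 onward already cover her.

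**The case against.** **The mark may have been lost when the PDF was read.** This is possible, since tables can break in extraction. But the total cholesterol row keeps its full set of column breaks before the Visit 9 mark, and the three adjacent lipid rows keep their Visit 3 marks. Loss of one mark is unlikely, though not excluded, and a look at the source page would settle it.

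**It is an obvious slip, and the Laboratory Manual will get it right.** The intent is indeed clear from the Synopsis and Section 2.4, and the manual, which was not available, may already include the test. That makes the consequence conditional. It does not make the table correct, and a laboratory or site working from Table 3 would be following the protocol.

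**Randomisation still allows a comparison of Visit 9 levels.** That is true, and such a comparison would be unbiased in principle. It is not the planned endpoint, it forgoes the baseline adjustment, and it cannot give the within-group mean changes that Section 12.2.1 also promises.

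**It is a minor endpoint.** This stands. Total cholesterol is one of four lipids under other objectives, and Section 12.2.1 treats even the secondary analyses as exploratory.

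**A stronger reading of the FSH timing.** A reader might infer that a woman on hormone replacement could be randomised and dosed before anyone knows whether the contraception and pregnancy-test requirements apply to her. The documents do not support this. By default they apply, and on the FSH route a late result can only release her from them. A value documented before the study may also suffice, and Table 1 repeats the eligibility check at Visit 3. Only the mismatch of timing between Table 3 and Section 3.1 remains.

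**Conclusion.** The point holds for total cholesterol. The protocol plans a baseline-adjusted comparison of change that its own sampling table cannot support. If Table 3 is followed as written, no patient of the 250 has a baseline value. That figure is a consequence of the schedule, not a forecast of what sites will do, and it rests on two assumptions: that the table reads on the page as it does in the text, and that neither the Laboratory Manual nor the LDL-C method brings in a Visit 3 measurement.

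The scope is narrow. A reader might take the gap as undermining the whole lipid objective, but HDL-C, LDL-C and triglycerides are scheduled correctly. The primary HbA1c analysis, the secondary efficacy analyses and the sample size are unaffected. It still deserves correction before patients reach Visit 3, because the repair costs almost nothing then and is impossible afterwards. The FSH timing is a small inconsistency to be tidied at the same time and carries no weight of its own here.

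**What to change.** In Table 3, add a mark for total cholesterol at Visit 3, and confirm that the Laboratory Manual and the central laboratory's Visit 3 panel include it. If patients have already passed Visit 3, ask the laboratory whether total cholesterol was reported with the other lipids. If it was not, state in the analysis plan, before unblinding, how this endpoint will be handled for those patients.

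In the same revision, reconcile the FSH mark in Table 3 with the Section 3.1 statement on when eligibility bloods are taken and assessed. Which passage should give way is for the sponsor to decide.

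The cost is a correction to one table and a check of one manual. The chemistry sample is already drawn at Visit 3, so there is no added visit or venepuncture.

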3. STUDY PLAN AND PROCEDURES

This Clinical Study Protocol has been subject to a peer review according to AstraZeneca's standard procedures.

3.1 Overall study design and flow chart

[figure not shown]
The following information relates to the key elements of the study design and where appropriate, the rationale behind their inclusion.

This study is a 24-week, multicentre, randomised, parallel-group, double-blind, placebo-controlled Phase IIIb study to evaluate the efficacy and safety of saxagliptin as add-on therapy to a stable metformin dose plus sulfonylurea compared to placebo as add-on therapy to a stable metformin dose plus sulfonylurea in patients with type 2 diabetes who have inadequate glycaemic control ($HbA_{1c} \geq 7\%$ and $\leq 10\%$). Patients should be on a stable combined dose of metformin extended release (XR) or immediate release (IR) (at MTD, with minimum dose for enrolment being 1500mg) and sulfonylurea (at MTD, with minimum dose for enrolment being $\geq 50\%$ of the maximum recommended dose) for at least 8 weeks prior to Visit 1.

This study will be conducted in the Asia Pacific region and the United Kingdom with a recruitment period of approximately 6 months. Approximately 275 patients need to be enrolled in order to reach the target of 250 randomised patients (males and females ≥ 18 years old with type 2 diabetes). The Overall Study Flow is presented in [Figure 1](#). The Study Plan is presented in [Table 1](#) and specifies the number, timing and routine assessments for the planned visits.

In order to minimise the number of screening failures entering Visit 2 patients will be pre-screened for HbA_{1c} – at Visit 1 (14 days prior to randomisation). Patients whose HbA_{1c} is $\geq 7\%$ and $\leq 10\%$, as confirmed by central laboratory, will undertake safety and other assessments at Visit 2 (7 days prior to randomisation) to confirm remaining eligibility criteria. Diet and exercise counselling will be provided at Visit 2 and again at randomisation. An Informed Consent Form based on all applicable regulatory requirements and laws will be provided to the patients and the study-related procedures and assessments explained. The Informed Consent Form must be signed before any study-related procedures or assessments are performed (e.g. collection of the blood sample for determination of HbA_{1c} at the central laboratory). Values outside the requested HbA_{1c} range is one of the main screening failure reasons and discrepancies between locally and centrally determined values are well known. All patients who are screened should be listed on a patient screening log.

Figure 1 Study flow chart for screening, enrolment period and double-blind treatment period

MTD: Maximum tolerated dose

* Minimum dose of metformin for enrolment = 1500 mg

** Minimum dose for sulfonylurea for enrolment is 50% of the maximum recommended dose:

Note: Patients will continue taking metformin and sulfonylurea at doses ascertained at enrolment, during the double-blind treatment period. Saxagliptin and Placebo will be administered as add-on therapy.

In this study, each patient will be enrolled on a stable combined dose of metformin XR or IR (MTD, with minimum dose for enrolment being 1500mg) and sulfonylurea (MTD, with minimum dose for enrolment being $\geq 50\%$ of the maximum recommended dose) for at least 8 weeks prior to Visit 1.

.Note: Patients must be on MTD of metformin IR or XR (minimum dose for enrolment being 1500 mg) and on MTD of sulfonylurea (minimum dose for enrolment being 50% of maximum recommended dose).

Following Informed Consent, patients will be pre-screened for HbA_{1c} – at Visit 1, within 14 days prior to randomisation. Patients whose HbA_{1c} is $\geq 7\%$ and $\leq 10\%$, as confirmed by central laboratory, will undertake safety and other assessments at Visit 2 (Day -7) to confirm remaining eligibility criteria. Patients who meet all of the inclusion criteria and none of the exclusion criteria will be randomised at Visit 3 and will commence the 24-week double-blind treatment period.

During the 24-week double-blind treatment period of the study, patients will still receive metformin and sulfonylurea at the dose ascertained during enrolment. In addition, patients will be randomised, at Visit 3, to receive the following:

- Double-blind saxagliptin 5 mg, orally, od or
- Double-blind matching placebo orally, od.

The study will consist of two periods:

Screening/enrolment period

Patients with type 2 diabetes who have inadequate glycaemic control (HbA_{1c} $\geq 7\%$ and $\leq 10\%$) and are currently on a stable combined dose of metformin XR or IR (MTD) and sulfonylurea (MTD) for at least 8 weeks prior to Visit 1 are eligible for enrolment. Blood samples for assessment of inclusion and exclusion criteria will be taken at Visit 1 and Visit 2 and assessed at the central laboratory before randomisation

Randomisation and double-blind treatment period

Patients with HbA_{1c} $\geq 7\%$ and $\leq 10\%$, as confirmed by the central laboratory and who meet all the inclusion and none of the exclusion criteria, will be randomised (1:1) at Visit 3 to one of the following two treatment groups:

- Double-blind saxagliptin (5 mg od) or
- Double-blind matching placebo

At Visit 3, either one tablet of double-blind 5 mg saxagliptin or a matching placebo tablet will be added to the metformin and sulfonylurea (same dose as being used at Visit 1) treatment.

The patient will return every 4 weeks (Visit 4 to Visit 9), and blood glucose measurements made by the patient since the last visit, the gastrointestinal tolerability and the FPG value (performed at the central laboratory) will be assessed.

Matching placebo tablets for saxagliptin will be given as appropriate for the 24-week double-blind treatment period of the study.

Fasting plasma glucose will be measured at the central laboratory every 4 weeks during the double-blind treatment period. The metformin and sulfonylurea doses must remain constant during the 24-week double-blind treatment period (Visit 3 to Visit 9) to ensure a steady state effect of the HbA_{1c} which is the primary endpoint of the study. Sulfonylurea may be down-titrated once in the case of major hypoglycaemic event or recurring minor hypoglycaemic events. (Refer to Section 5.8). Titration (up or down) of study medication during the treatment period (Visit 3 to Visit 9) is prohibited. Blood samples for the assessment of the glycaemic parameters (based on results from the central laboratory) will be taken at each visit to determine if criteria for discontinuation of the investigational product are met. The patients will be instructed to monitor their fasting blood glucose levels at least every other day and to register the values associated with hypoglycaemic events into their patient diary.

During the double-blind treatment period, dietary and lifestyle modification will be re-enforced.

Finally, randomised patients who do not complete the study should complete the procedures described for Visit 9 (End of Study Visit).

Table 1 Study plan for screening, enrolment period and double-blind treatment period

Study period	Screening / Enrolment		Double-blind treatment period						
	Enrolment	Screening	Randomisation						
Visit label	1	2	3	4	5	6	7	8	9a
Visit number	1	2	3	4	5	6	7	8	9a
Study Week	-2	-1	1	4	8	12	16	20	24
Study Day	-14 to -10	-9 to -5	0	28	56	84	112	140	168
Visit Window (No. days relative time Visit 3)		-		28±3	56±3	84±3	112±3	140±3	168±3
Informed consent	X								
Blood sample for HbA1c	X		X	X	X	X	X	X	X
Demography and medical history		X							
Weight		X	X	X	X	X	X	X	X
Height		X							
Waist circumference			X						X
Inclusion/exclusion criteria	X	X	X						
Physical examination		X							X
Brief physical examination			X	X	X	X	X	X	
Vital signs		X	X	X	X	X	X	X	X
12-lead ECG			X						X
Concomitant medication		X	X	X	X	X	X	X	X
Laboratory assessmentsb		X	X	X	X	X	X	X	X
Pregnancy testc		X	X	X	X	X	X	X	X

Study period	Screening / Enrolment		Double-blind treatment period						
	Enrolment	Screening	Randomisation						
Visit label	1	2	3	4	5	6	7	8	9a
Visit number	1	2	3	4	5	6	7	8	9a
Study Week	-2	-1	1	4	8	12	16	20	24
Study Day	-14 to -10	-9 to -5	0	28	56	84	112	140	168
Visit Window (No. days relative time Visit 3)		-		28±3	56±3	84±3	112±3	140±3	168±3
Dispense/Return investigational products			X	X	X	X	X	X	X
Dispense/Return glucometer and/or supplies/provide instruction		X	X	X	X	X	X	X	X
Dispense patient diary		X	X	X	X	X	X	X	
Patient diary review for hypoglycaemic events/check glucose values in glucometer			X	X	X	X	X	X	X
Patient reported outcome questionnaire			X						X
Adverse events (AEs)	X	X	X	X	X	X	X	X	X
Drug accountability			X	X	X	X	X	X	X

- Randomised patients who do not complete the study should complete the procedures described for the end of the double-blind treatment period (Visit 9 [End of Study Visit]).
- Specification of laboratory parameters is presented in Section 6.3.1 (efficacy) and Section 6.4.5 (safety).
- Pregnancy test will be performed on all women of childbearing potential.
- Patient reported outcome questionnaire: Euro Quality of Life-5 Dimension (EQ-5D).

